# 5.5.1 Clinical Procedures

- Update locator information.
- Review Daily Study Records and note the time of last product application; review instructions for completion of Daily Study Records if needed.
- Count used and unused product tubes and conduct adherence interview. Store used tubes until end of study. If space does not allow storage, then document the count and disposal.

- Perform pelvic examination including:
  - speculum examination of vagina and cervix,
  - collect pH sample from the vaginal wall,
  - collect swab from anterior or lateral fornix for:
    - one dried smear (smear specimen on slide and allow to air dry),
    - wet prep (two samples of discharge on slide for saline prep, potassium hydroxide prep and whiff test),
  - ➢ bimanual examination for adnexal masses or tenderness.
  - if abnormal vaginal discharge or purulent cervicitis is noted, collect urine for *N. gonorrhoeae* and *C. trachomatis* LCR assay.
  - ➢ if ulcerative lesions are noted:
    - photograph lesions according to procedures in Appendix V.
    - collect swabs for syphilis dark field microscopy (on-site) and M-PCR for HSV-2, H. *ducreyi* and *T. pallidum*. (at the HPTN Central Lab)
    - label digital image with location/image number.
- If symptomatic, collect urine for dipstick urinalysis.
- Provide instruction for follow-up care and product use, or not, as appropriate.
- Instruct participant to contact or return to the study site if she experiences discomfort, discolored or malodorous discharge, or other AEs.
- Provide Daily Study Records and review instructions for completion.
- Distribute additional study supplies if needed.
- Schedule Day 14 Follow-up Visit.
- Complete all required data collection forms.

# 5.5.2 Laboratory Procedures

- Record results of dipstick urinalysis and process urine culture if dipstick positive for UTI.
- Record vaginal pH measurement.
- Examine wet mount by direct microscopy to detect *T. vaginalis*, *C. albicans* infections, and clue cells for BV.
- Conduct LCR for *N. gonorrhoeae* and *C. trachomatis* if symptomatic.
- If ulcerative lesion was observed, conduct dark field microscopy of swab and serology (RPR with confirmation by FTA-ABS or TP/HA) for *T. pallidum* and prepare and ship swabs to the HPTN Central Lab for M-PCR.
- Store unstained dried smear for Gram staining and batch analysis using the Nugent criteria for BV.

# 5.6 Day 14 Follow-up Visit for Female Participants (Target Day 14, allowable Day 12-16)

This visit is scheduled to take place on study Day 14. Every effort should be made to complete this visit on Day 14, however the visit may take place — if necessary —between Days 12 and 16. As described below, the baseline evaluations completed at the study Screening and Enrollment Visits, including routine colposcopy, are repeated at this visit. Diagnosis and follow-up of any observed abnormalities will proceed according to Appendix III.

# 5.6.1 Clinical Procedures

- Update locator information.
- Administer Follow Up Acceptability Assessment.
- Review Daily Study Records and note the time of last product application.
- Count the number of used and unused product tubes and conduct adherence interview. Store used tubes until end of study. If space does not allow storage then document the count and disposal.
- Collect urine for leukoesterase screen (if symptomatic) and culture if screen positive for WBCs.
- Perform pelvic examination with colposcopy (according to Appendix V) including:
  - > speculum examination of vagina and cervix,
  - colposcopic examination of the vaginal and cervical mucosa for lesions,
  - take colposcopic digital image(s) without filter, encompassing the cervix and fornices,
  - collect pH sample from vaginal wall,
  - Collect swab from anterior or lateral fornix for:
    - one dried smear (smear specimen on slide and allow to air dry),
    - wet prep (two samples of discharge on slide for saline prep, potassium hydroxide prep and whiff test),
  - bimanual examination for adnexal masses or tenderness.
  - if abnormal vaginal discharge or purulent cervicitis is noted, collect urine for *N. gonorrhoeae* and *C. trachomatis* LCR assay.
  - ➢ if ulcerative lesions are noted:
    - photograph lesions according to procedures in Appendix V.
    - collect swabs for syphilis dark field microscopy (on-site) and M-PCR for HSV-2, *H. ducreyi* and *T. pallidum*. (at the HPTN Central Lab)
- If symptomatic, collect urine for dipstick urinalysis.
- Provide instruction for follow-up care as appropriate.
- Collect blood specimens for hematology, liver and renal function, APTT/PT and PRO 2000/5 analysis.

- Instruct participant to contact or return to the study site if she experiences discomfort, discolored or malodorous discharge, or other AEs within the next week.
- Schedule focus group visit.
- Label digital image with location/image number.
- Complete all required data collection forms.

## 5.6.2 Laboratory Procedures

- Record results of urine pregnancy test.
- Record results of dipstick urinalysis and process urine culture if dipstick positive for UTI.
- Record vaginal pH measurement.
- Examine wet mount by direct microscopy to detect *T. vaginalis*, *C. albicans* infections, and clue cells for BV.
- Conduct LCR for *N. gonorrhoeae* and *C. trachomatis* if symptomatic.
- If ulcerative lesion was observed, conduct dark field microscopy of swab and serology (RPR with confirmation by FTA-ABS or TP/HA) for *T. pallidum* and prepare and ship swabs to the HPTN Central Lab for M-PCR.
- Store unstained dried smear for Gram staining and batch analysis using the Nugent criteria for BV.
- Conduct complete blood count, APTT/PT, liver and renal function tests.
- Prepare plasma samples for determination of study drug levels for batch shipping at the end of the study.
- Archive plasma and serum.

#### 5.7 Interim Contacts and Visits (ad hoc)

Interim contacts and visits may be performed at participant request at any time during the study. All interim contacts and visits will be documented in participants' study records and on applicable case report forms.

Some interim visits may occur for administrative reasons. For example, the participant may have questions for study staff or require additional study supplies. Other interim contacts and visits may occur in response to AEs experienced by study participants.

When interim contacts or visits are completed in response to participant reports of AEs, study staff will assess the reported event clinically and provide or refer the participant to appropriate medical care; all AEs associated with genital symptoms will be evaluated according to the pelvic exam — with colposcopy — procedures described for the Day 2 and 14 Follow-up Visits, and diagnosis and follow-up of any observed abnormalities will proceed according to Appendix III.

#### 5.8 Focus Groups

Female study participants will take part in focus groups within approximately four weeks after completing product use, to elicit information on product acceptability and considerations for product use that may not emerge through individual questionnaires. Willingness to participate in the focus group discussions is not required. However, every effort will be made to obtain feedback from the participants. All participants will be asked individually regarding their interest and any possible concerns they may have with taking part in the groups. Participants may choose to participate in a one-on-one session rather than a group session, discuss their feelings with the interviewer by telephone, or complete a detailed questionnaire. Male sexual partners also will be invited to take part in roughly concurrent — but separate — focus groups. Each focus group will include approximately 3-7 participants. Dyads will be held at the wish of the participants. Each group will be conducted according to the following established principles:

- A trained facilitator will lead each group according to an interview guide based on a standard set of relevant questions.
- The facilitator will permit broad and equitable discussion among group participants.
- Each session will be audio-taped and transcribed for qualitative content analysis.

No personal identifying information will be collected during focus groups.

#### 6.0 Adverse Event Reporting Requirements

An AE is defined as any untoward medical occurrence in a clinical research participant administered an investigational product and which does not necessarily have a causal relational with the investigational product. As such, an AE can be an unfavorable or unintended sign (including an abnormal laboratory finding, for example), symptom or disease temporally associated with the use of an investigational product, whether or not considered related to the product.

Study participants will be provided a 24-hour telephone number and instructed to contact the study clinician to report any AEs they may experience, except for life-threatening events, for which they will be instructed to seek immediate emergency care. Depending on the severity of the event, the clinician will instruct the participant to present to the study site (for more mild events) or to an emergency room (for more serious events) for immediate evaluation. Where feasible and medically appropriate, participants will be encouraged to seek medical care where the study clinician is based, and to request that the clinician be paged or otherwise contacted upon their arrival. With appropriate permission of the participant, records from all non-study medical providers related to AEs will be obtained and required data elements will be recorded on study case report forms. All participants reporting an AE will be followed clinically, until the AE resolves (returns to baseline) or stabilizes.

Study site staff will document on study case report forms all AEs reported by or observed in enrolled study participants regardless of severity and presumed relationship to study product. All AEs will be defined as described in the DAIDS HPTN SAE Reporting Manual (dated June 1, 2001). All AEs will be graded using the DAIDS Table for Grading Severity of Adverse Experiences (also referred to as the "Toxicity Table"). Both the DAIDS SAE Reporting Manual and the Toxicity Table are provided in the studyspecific procedures manual. The investigator or designee will assess the relationship of all AEs to the study product based on the DAIDS HPTN SAE Reporting Manual, the Investigator's Brochure, and his/her clinical judgment.

Site staff also will report all AEs that meet serious adverse event (SAE) reporting requirements according to the procedures set forth in the Study-Specific Procedures Manual and the time frames set forth in the DAIDS HPTN SAE Reporting Manual. Specifically, DAIDS-defined "intensive" reporting requirements will be followed for this study. Information on all AEs will be included in reports to the US Food and Drug Administration (FDA), and other applicable government and regulatory authorities, such as the DCGI. Site staff will report information on all AEs and SAEs to their EC in accordance with all applicable regulations and local EC requirements.

Note: The above-stated reporting requirements apply to enrolled female study participants. Participants and their male partners will be instructed to report AEs experienced by male partners to the study clinician, who will evaluate and document the event, as well as provide follow-up care or refer the partner for such care. In the event that a male partner experiences an AE that meets SAE reporting requirements, the event will reported as an SAE according to the procedures set forth in the Study-Specific Procedures Manual and the time frames set forth in the DAIDS SAE Reporting Manual.

#### 7.0 Statistical Considerations

#### 7.1 General Design

This is a Phase I open-label study with 14 days of twice daily application of 0.5% PRO 2000/5 Gel (P) and follow-up for each study participant. Safety will be assessed after 7 and 14 days of product use. Acceptability measures will be assessed at baseline and after 14 days of product use via standardized questionnaire; additional acceptability information will be collected through focus groups with female study participants and their male sexual partners conducted approximately 2-3 weeks after completing the product use regimen.

#### 7.1.1 Primary Endpoints

Consistent with the primary study objective to assess the safety of 0.5% PRO 2000/5 Gel (P) when administered twice daily for 14 consecutive days on the vulvar and cervicovaginal mucosa, the following primary endpoints — that warrant discontinuation of product use — will be assessed:

- Macroscopic evidence of damage (determined not to be due to pathogen or mechanical trauma) to the vulvar and/or vaginal epithelium including ulceration and other lesions, abrasion, severe erythema, and/or severe edema.
- Macroscopic evidence of damage (determined not to be due to pathogen or mechanical trauma) to the cervical mucosa including ulceration and other lesions, abrasion, severe erythema, and/or severe edema.
- Laboratory evidence of grade 3 or higher toxicity for hematology, liver or renal function (as defined by the DAIDS Toxicity Tables) which cannot be directly attributed to another cause after consultation with the protocol chairs, the study site clinician, the medical officer, statistician, and the protocol specialist.

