#### Implementation

This Letter of Amendment does not affect the study design or the informed consents being used in the study. If the HPTN 047 protocol is amended in the future, this Letter of Amendment will be incorporated into the next version.

The following protocol modifications, indicated by strikethrough or under-scored text, are made to the HPTN 047 Protocol.

**1.** Section 3.0 Study Population, 3rd sentence

Participants will be selected for this study according to the inclusion and exclusion criteria in Sections 3.1.1 and 3.2.1. Participants will be designated as low risk or high risk for HIV infection based on the definitions found in sections 3.1.2 and 3.2.2.

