## 3.2.2 Definition for Female Participants at Low Risk for HIV Infection

- In addition to the exclusion criteria specified in Section 3.2.1, Female participants women will not be defined excluded from the study as at low risk for HIV infection participants if they meet any of the following <del>criteria</del> (based on participant knowledge and self-report):
  - Have been diagnosed and/or treated for an STD (other than HIV) or pelvic inflammatory disease in the three months prior to screening.
  - Have a current male sexual partner who was diagnosed or treated for an STD (other than HIV) in the three months prior to screening.
  - Have a current male sexual partner who has injected non-therapeutic drugs in the three months prior to screening.
  - Have signs, as seen on a pelvic exam or colposcopy, consistent with an STD, other genital tract infection – other than bacterial vaginosis (BV) – or trauma.
    - → Vaginitis
    - → Cervicitis
    - → Edema
    - → Erythema
    - → Ecchymosis
    - Petechial hemorrhage
    - → Vulvar or cervicovaginal lesions, ulcers, abrasions
    - Subepithelial hemorrhage and swelling and
    - Laboratory findings indicative of genital tract infection other than asymptomatic BV

Note: Signs of a asymptomatic BV include the presence of white to grey homogeneous discharge, positive whiff test (amine odor) with addition of KOH, pH >4.5, presence of clue cells, decrease in lactobacilli morphotypes, and increase in non-lactobacilli morphotypes. Women with clinical or gram stain evidence of BV and symptoms (discharge, odor, itching) at screening should be treated and re-evaluated for inclusion in the low risk participants. Women without symptoms, but with clinical or gram stain evidence of BV, or asymptomatic yeast colonization, are eligible as low risk participants.

3. Section 3.2.3 renamed Exclusion Criteria for Male Partners of Female Participants

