#### 3.2 Exclusion Criteria

#### **3.2.1** All Female Participants

Women who meet any of the following criteria by self-report at screening or enrollment, unless otherwise specified, will be excluded from this study:

Note: Women with observed abnormalities as described below will be referred for appropriate clinical follow-up and/or treatment. Since all potential participants are eligible for India's national health service, further clinical care will be provided at no cost to the participant.

- Are menopausal.
- Are currently breastfeeding.
- Are currently using, or within the year prior to screening have used, non-therapeutic intravenous drugs.
- Are pregnant (based on a urine pregnancy test).
- Have one or more grade 3 or higher liver, renal, or hematology abnormalities, as defined by the Division of AIDS (DAIDS) Toxicity Tables at screening.
- Have a positive urine culture.
- Have a clinically detectable genital abnormality (i.e., vulvar, vaginal, cervical and/or perianal ulcer and/or lesion).
- Have a history of adverse reaction to anticoagulant(s).
- Have a history of sensitivity/allergy to latex.
- Have used any spermicide or spermicidally lubricated condom within the past week (prior to enrollment).
- Have participated in any other investigational drug trial within 30 days prior to screening .
- In the three months prior to screening have (any of the following):
  - used an intrauterine contraceptive device,
  - ▹ had an abnormal Pap smear,
  - ▹ been pregnant,
  - ➢ had gynecologic surgery,
  - ➢ had breakthrough menstrual bleeding, or
  - ➤ had vaginal bleeding during or following sexual intercourse.

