# 5.2.1 Clinical Procedures

- Update locator information.
- Provide results of HIV and STD tests and post-test counseling.
- Review practice Daily Study Records for completeness and accuracy.
- Document that the participant's partner has provided informed consent.
- Complete Initial Acceptability Assessment.
- Collect urine for HCG pregnancy test; provide participant with result.
- Collect urine dipstick urinalysis (if symptomatic) and process urine culture if dipstick positive for urinary tract infection (UTI).
- If symptomatic, collect urine for *N. gonorrhoeae* and *C. trachomatis* LCR assay.
- Perform pelvic examination with colposcopy (according to Appendix V) including:
  - speculum examination of vagina and cervix,
  - colposcopic examination of the vulva, vaginal and cervical mucosa,
  - take baseline colposcopic digital image(s) without filter, encompassing the cervix and fornices,
  - collect pH sample from the vaginal wall,
  - collect swab from anterior or lateral fornix for:
    - one dried smear (smear specimen on slide and allow to air dry),
    - wet prep (two samples of discharge on slide for saline prep, potassium hydroxide prep and whiff test), and
  - ➢ if ulcerative lesions are noted
    - photograph lesions according to procedures in Appendix V
    - collect swabs for syphilis dark field microscopy (on-site) and M-PCR for HSV-2, *H.ducreyi* and *T. pallidum* (at the HPTN Central Lab)
    - collect blood for syphilis serology
  - bimanual examination for adnexal masses or tenderness.
- Collect blood for hematology, liver and renal function, APTT/PT, PRO 2000/5 analysis and plasma and serum archive.
- Provide instructions for product administration (see Appendix IV).
- Observe first product administration (if desired by participant).
- Provide Daily Study Records and instructions for completion.
- Count and record total number of tubes of study product dispensed to the study participant.
- Distribute study product and applicators (2 kits), condoms and panty liners.
- Instruct participant to return all used and unused tubes and applicators to the clinic at her Day 2 visit.

- Instruct participant on anticipated amount, consistency and color of discharge due to gel expulsion.
- Instruct participant to distinguish between discolored or malodorous discharge and the discharge anticipated with use of study product.

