#### 7.4.1 Primary Analyses

Primary data analyses will tabulate the number of primary endpoints listed in Section 7.1.1 — observed during the study. All participants who enroll in the study will be included in each tabulation. Individual participants will contribute once to the calculation of event rates. Additional safety analyses will tabulate the number and type of AEs observed overall and by severity and relationship to product. AEs that lead to discontinuation of product use and/or study participation will be tabulated separately. The temporal relationship of product application and AE onset, and the duration of symptoms, also will be evaluated. Finally, baseline and Day 14 laboratory measures will be summarized and the change in function, defined as the difference between the baseline and Day 14 measurements, will be described.

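### The two mucosal primary endpoints do not require a finding to be new or worse than at the Day 0 colposcopy, so damage present before the first dose may be counted as a primary event

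*Protocol*

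**What the plan says.** Protocol 7.1.1 defines two mucosal primary endpoints, one for the vulvar and vaginal epithelium and one for the cervix. The cervical one reads "Macroscopic evidence of damage (determined not to be due to pathogen or mechanical trauma) to the cervical mucosa", and the findings that count are damage "to the cervical mucosa including ulceration and other lesions, abrasion, severe erythema, and/or severe edema". The vulvar/vaginal bullet has the same structure. The lead-in describes the endpoints as ones that warrant stopping the product.

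Section 7.4.1 fixes the count: "Primary data analyses will tabulate the number of primary endpoints listed in Section 7.1.1", as observed during the study. It adds that "All participants who enroll in the study will be included in each tabulation", and each woman contributes once.

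On the state of the mucosa before dosing:

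- Section 3.2.1 excludes all women who "Have a clinically detectable genital abnormality (i.e., vulvar, vaginal, cervical and/or perianal ulcer and/or lesion". It does not name abrasion, erythema or edema.
- Section 5.2.1 requires, at the Enrollment Visit and before the first dose, "colposcopic examination of the vulva, vaginal and cervical mucosa", with baseline images.
- Version 2.0 of 3.2.2 itemized edema, erythema and abrasions as exclusions for low-risk women only, in addition to 3.2.1.
- The Letter of Amendment of 3 November 2003 deletes that list and calls it redundant to the seventh bullet of 3.2.1. It says "Participants will be designated as low risk or high risk for HIV infection" on the basis of 3.1.2 and 3.2.2. The retained 3.2.2 bullet opens "Have signs, as seen on a pelvic exam or" and goes on to name colposcopy; it now decides only whether a woman is low risk.

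**The concern.** The study has no control arm, so the only comparison that can separate damage arising under the gel from damage already present is each woman's own Day 0 examination. That examination is done with full colposcopy, but the mucosal endpoints do not refer to it. As worded, they count what is present at follow-up, with two named causes removed.

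The laboratory endpoint is better protected. It has an open attribution rule (no other direct cause), and 3.2.1 excludes women with grade 3 or higher liver, renal or hematology abnormalities at screening, which is the endpoint's own threshold. The mucosal endpoints have no equally clear match between what is excluded at entry and what counts later.

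At stake is the primary event rate. The Day 2 colposcopy comes after only two days of use, so a finding present at Day 0 could still be visible then. One carried-over finding is enough to make a woman an event. Any resulting bias is upward: it would not hide harm, but it could wrongly burden the safety conclusion.

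**Working it through.** **Step 1. Does the text require a comparison with Day 0?** The conditions in 7.1.1 are macroscopic damage, a named type of finding, and not due to pathogen or mechanical trauma. The conditions in 7.4.1 are observed during the study, all enrolled women, once per woman. None refers to Day 0.

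**Step 2. Does eligibility make the baseline clean?**

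- Pointing to yes: the November 2003 Letter calls the erythema/edema/abrasion list redundant to 3.2.1, and Appendix V Table 2 lists abrasion, erythema and edema in a table of lesion characteristics.
- Pointing to no: 3.2.1 itself names only ulcers and lesions. Section 7.1.1 lists abrasion, severe erythema and severe edema beside other lesions, as separate items. Version 2.0 of 3.2.2 also named them separately, and for low-risk women only. Amended 3.2.2 uses examination signs to designate risk, which would have little to classify if every such sign already barred enrollment.

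Ulcers and lesions are covered for all women. For the other three findings the documents do not agree.

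**Step 3. The plan's own figures.** Section 7.2 tabulates the probability of two or more events in n = 60:

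Pr(2+) = 1 − (1 − p)^n − n·p·(1 − p)^(n−1)

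For p = 1%, 5%, 7%, 10%, 15% and 20% this gives 0.121, 0.808, 0.929, 0.986, 0.999 and 1.000, against the printed .12, .81, .93, .99, >.99 and >.99. The adherent-subgroup statements also reproduce: n = 54 at 7% gives 0.899, and n = 48 at 8% gives 0.906. The sample-size figures are correct.

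**Step 4. Effect of carried-over findings.** Let g be the true gel rate and b the proportion of women with a qualifying Day 0 finding that persists to follow-up, independent of g. The counted rate is 1 − (1 − g)(1 − b), which equals b when g = 0. The documents give no value of b, so the values below are assumptions.

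Example with g = 0, b = 5%, n = 60: 0.95^60 = 0.0461; 60 × 0.05 × 0.95^59 = 0.1455; Pr(2+) = 1 − 0.0461 − 0.1455 = 0.808.

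| Assumed b, no gel effect | Expected events, all 60 affected | Pr(2+) | Expected events, only the 30 higher-risk affected | Pr(2+) |
|---|---|---|---|---|
| 0% | 0 | 0 | 0 | 0 |
| 2% | 1.2 | 0.34 | 0.6 | 0.12 |
| 5% | 3.0 | 0.81 | 1.5 | 0.45 |
| 10% | 6.0 | 0.99 | 3.0 | 0.82 |

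With a real gel rate of 5% and b = 5% in all 60 women, the counted rate is 1 − 0.95 × 0.95 = 9.75%. That is 5.85 expected events instead of 3.0.

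**Step 5. Effect on the interval.** Section 7.4 plans exact confidence intervals. The upper 95% limit for 0/60 is 1 − 0.025^(1/60) = 6.0%. Three carried-over findings make it 3/60, with an upper limit of 13.9%.

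**Step 6. With the condition added.** The counted rate is g, and the 7.2 table applies as printed. If b = 0, adding the condition changes nothing.

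**The case against.** A reader might infer that abrasion or severe erythema at Day 0 is certain to be counted as gel toxicity, and that the primary rate is therefore biased. The documents do not support that certainty.

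- **Eligibility may already remove these women.** The November 2003 Letter reads the all-women exclusion as covering erythema, edema and abrasion. The Day 0 colposcopy serves to confirm eligibility (2.3), and procedures stop if a woman is found ineligible (5.2). This stands as one reasonable reading, under which b is 0. It does not settle the matter, because the text of 3.2.1 was not changed to say so.
- **The endpoint's own filter would catch some findings.** The retained 3.2.2 bullet concerns signs consistent with infection or trauma, and 7.1.1 removes pathogen and mechanical trauma. Abstinence for 48 hours before enrollment also reduces traumatic findings. This narrows the gap, but a baseline finding with no established cause still passes.
- **The lead-in to 7.1.1 may restrict the count.** Appendix III has the product continue for abrasion unless re-evaluation shows it significantly worse. On that reading an abrasion merely still visible at Day 2 would not be an event. The two passages need reconciling; this review takes no position on which should govern. The argument does not reach generalized erythema or severe edema, for which Appendix III requires no worsening.
- **Baseline comparisons are planned elsewhere.** Section 7.4 names McNemar's test, and Appendix VIII has change tables for pelvic and colposcopic findings and a treatment-emergent adverse event table. These would help expose carried-over findings, but none alters the primary count. The SAP, which is not shown, may add such a rule; the endpoint and its counting are nevertheless fixed in the protocol.
- **The prevalences are hypothetical.** This stands. The all-60 column is the less likely case, since Version 2.0 itemized these findings as exclusions for low-risk women.

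The two-event probability is also easily over-read. It is the detection probability of 7.2, not a decision rule on these endpoints. The suspension rule in 7.3 concerns grade 3 or higher adverse events judged related to the product.

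**Conclusion.** The concern holds as a gap in the definition of the primary endpoint. The two mucosal endpoints lack a new-or-worse-than-Day-0 condition, and the documents conflict on whether abrasion, severe erythema or severe edema at Day 0 bars enrollment. A pre-existing finding may therefore be counted as a primary event, most plausibly in a higher-risk woman.

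The size cannot be fixed from the documents. It runs from nothing, if eligibility works as the Letter of Amendment implies, to an 0.82 chance of two or more spurious events if 10% of the 30 higher-risk women carry a persistent qualifying finding, and 0.99 if 10% of all 60 do. These figures assume no gel effect, persistence to follow-up, and no removal of the findings as due to pathogen or trauma. The change is worth making because it costs little and removes a possible upward bias; the gap does not invalidate the safety assessment.

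**What to change.** 1. In both mucosal bullets of 7.1.1, count a finding only if it was absent at that site on the pre-dose Day 0 colposcopy or is worse than at Day 0 (for example superficial to deep disruption, or mild or moderate to severe).
2. Add a line to the primary table listing separately the women whose qualifying finding was already present at Day 0.
3. Reconcile 3.2.1, amended 3.0 and 3.2.2, and the redundancy statement in the November 2003 Letter, so that they give one answer on whether abrasion, erythema and edema are exclusionary for all women. Reconcile the 7.1.1 lead-in with the abrasion row of Appendix III at the same time.

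The cost is one clause, one table line and an editorial reconciliation; the Day 0 findings and images are already collected. The small downside is that a pre-existing finding which the gel merely keeps from healing is no longer counted, but the separate listing shows it.
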